3.7 Research Indicators

The objective of this study was to evaluate the efficacy and safety of anlotinib combined with sintilimab as first-line treatment for non-hepatic metastatic advanced colorectal cancer. The primary efficacy endpoint was overall response rate (ORR), while secondary efficacy endpoints included safety (assessed using CTCAE 5.0), progression-free survival (PFS), overall survival (OS), and disease progression rate (DPR). Concurrent biomarker analysis was performed.

3.7.1 Efficacy Indicators

Objective response rate (ORR) refers to the proportion of patients whose tumors shrink to a certain extent and sustain this reduction for a specified duration (primarily for solid tumors). It encompasses cases of complete response (CR) and partial response (PR).

Deepness of response (DpR): This refers to the percentage of maximum tumor shrinkage achieved during treatment compared to baseline. If a complete response (CR) is observed, the DpR is 100%.

Tumor response and disease progression will be assessed by investigators according to the RECIST criteria.

Progression-free survival (PFS) refers to the time from enrollment until tumor progression or death.

Overall survival (OS) refers to the time from randomization to death from any cause.

The duration of response maintenance was calculated for all patients who achieved confirmed RECIST-standardized PR or CR. The response maintenance period was defined as the time from the first recorded PR or CR until death or disease progression (whichever occurred first). For patients who were still alive and disease-free as of the analysis date, the cutoff date was set as the date of their last radiological assessment.

This study also explores the relationship between molecular markers and therapeutic efficacy and safety.

3.7.2 Safety Indicators

All patients who have received at least one dose of the investigational drug will be included in the safety analysis as the valid population. The physical examination results, vital signs, adverse events, and abnormal laboratory test values of the patients will be summarized. All adverse events should be reported and graded according to the Common Terminology Criteria for Adverse Events (CTCAE) version 5.0.

3.7.3 Evaluation Period

The study was started on the date of signing the informed consent form.

3.7.3.1 Research Visits

- Screening visit should be conducted within 28 days prior to initiation of study drug therapy.
- The treatment period refers to the duration from the initiation of the first study drug administration until the patient discontinues the study drug therapy.
- Patients were evaluated every 8 weeks after discontinuation of study drug therapy due to non-progressive conditions. If disease progression was confirmed, they would enter the follow-up period. During this period, contact with patients should be maintained every 3 months until the patient's death was recorded, to collect data on overall survival.

3.7.3.2 Imaging Evaluation

- Screening period: A CT or MRI scan of the chest and abdomen must be performed at least 28 days prior to enrollment, and tumor measurements must be recorded in the CRF according to RECIST criteria.
- Treatment phase: CT or MRI scans should be performed at least every 6 weeks ±

5 days to evaluate the lesion, and tumor measurements should be recorded in the CRF according to RECIST criteria. Additional examinations should be conducted based on symptomatic indications.

- At the end of the study: CT or MRI scans were performed to evaluate the lesions, and tumor measurements were recorded in the CRF according to the RECIST criteria. Additional examinations were conducted based on symptomatic indications.

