3.8 Research Process

3.8.1 Screening Period

within 28 days prior to initiating the study drug

- Sign an informed consent form before any research-related procedure is performed;
- baseline 12-lead electrocardiogram (ECG) examination;
- Brain CT or MRI scans should only be performed when neurological symptoms are present (indicating brain metastases).
- Tumor assessment at baseline: At least one CT or MRI scan of the target lesion, which can be performed within 28 days prior to initiating the investigational drug.

Screening period – within 7 days prior to initiating study drug therapy

- Record/confirm the tumor stage at the time of diagnosis.
- Demographic information, complete medical history, and surgical history, including previous anticancer treatments.
- A complete physical examination (PE), including the ECOG general condition score, height, weight, and a detailed systemic examination.
- Signs and symptoms (including heart rate, blood pressure, respiratory rate, and body temperature).
- Record all comorbidities and concomitant medications with their indications.
- Complete blood count (CBC): hemoglobin, platelet count, white blood cell count and differential, including absolute counts of neutrophils and lymphocytes.
- Complete blood biochemistry panel: including blood glucose, calcium, phosphorus, sodium, potassium, chloride, creatinine, blood urea nitrogen

(BUN), total protein, albumin, alanine aminotransferase (ALT), aspartate aminotransferase (AST), alkaline phosphatase, total bilirubin, etc.

- Urinary pregnancy tests should be performed for all women of childbearing age. Women who have been postmenopausal for at least 1 year or have undergone sterilization procedures are not required to undergo pregnancy testing.
- Urinalysis: Includes urine leukocytes, urine red blood cells, urine glucose, urine protein, and occult blood
- Routine stool examination

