Efficacy Evaluation: All patients will undergo one of the following efficacy evaluations:

Complete remission (CR): All clinical and imaging evidence of the tumor (including target and non-target lesions) is eliminated.

Partial response (PR): A reduction of at least 30% in the sum of LD values at the target lesion compared to baseline total LD.

Stable Disease (SD): A stable state of the disease. The lesion has not met the PR criteria for shrinkage or has not met the PD criteria for progression.

Disease progression (PD): Referring to the minimum total LD value recorded from the start of treatment, the sum of LD in the measured lesions increases by at least 20% or one or more new lesions appear. The emergence of any new lesions indicates disease progression. In special cases, unmeasurable lesions with clear progression may also be accepted as evidence of disease progression.

Evaluation of therapeutic efficacy for target lesions versus non-target lesions

Target lesion	Non-target lesions	New lesion	Overall response	This type of optimal response also requires
CR	CR	not have	CR	Confirm after 4 weeks
CR	Non-CR/Non-PD	not have	PR	Confirm after 4 weeks
PR	Non-PD	not have	PR	
SD	Non-PD	not have	SD	At least 4 weeks from the baseline period
PD	any	Present or absent	PD	No SD, PR, or CR had occurred previously.
any	PD	Present or absent	PD	

any	any	have	PD	
-----	-----	------	----	--

Patients with an overall deterioration in health status requiring treatment discontinuation should be reported as 'symptom exacerbation' if there is no objective evidence of disease progression at this time. Objective disease progression should be observed and documented as closely as possible even after treatment cessation.

Relief time

The duration of remission should be calculated from the time of the first meeting of the criteria for CR or PR (whichever is recorded first) until the date of the first recorded disease recurrence or progression.

disease stable time

The duration of disease stability should be calculated from the start of treatment until disease progression is achieved, with the minimum measured lesion size after treatment initiation serving as the reference.

measuring method

The same evaluation criteria and measurement techniques should be used to describe and report each designated lesion during both the baseline and follow-up periods.

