Clinical lesions — Clinical lesions are considered measurable only when located on the body surface (e.g., skin nodules, palpable lymph nodes). For dermatological lesions, it is recommended to document them with color photographs including the lesion and the measuring ruler used.

Chest X-ray — When the lesion has well-defined margins and is surrounded by air-filled lung tissue, the lesion observed on chest X-ray may be considered measurable. However, CT should still be the preferred modality.

CT/MRI — CT and MRI are currently the most feasible and reproducible methods for measuring target lesions selected for response evaluation. Conventional CT and MRI should be performed with continuous scanning at a slice thickness of 10 mm or less. Spiral CT should be performed with continuous scanning at a slice thickness of 5 mm and reconstruction. This method is suitable for the chest, abdomen, and pelvis. Scanning of the head, neck, and limbs often has specific requirements.

When measurable tumor lesions meet the criteria for remission and disease stability, cytological examination must be performed for any effusion that occurs or worsens during

treatment to confirm whether it is tumor-induced (the effusion may be a side effect of treatment), thereby distinguishing between disease remission/stability and disease progression.

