7.5 Research Process Table

Flowchart of Therapy Process

	pretherapy	Each 3-week period constitutes one cycle.			Post-treatment follow-up visit	Follow-up after treatment discontinuation due to non-progressive conditions until disease progression	Follow-up after progression 9
		Cycle 1	Cycle 2	The 4th and subsequent cycles until disease progression or treatment discontinuation			
Operation item	Filter period	Day 1	Day 1	Day 1	Within 7 days	Every 8 weeks	Every 3 months
Informed Consent Form	X (within 28 days)						
Medical History 1	X (within 7 days)						
Complete physical examination 2	X (within 7 days)						
Inclusion/Exclusion Criteria	X						
stochastic	X						
Life signs and ECOG score	X	X	X	X	X	X	
12-lead electrocardiogram	X (within 28 days)		X	X	X		
Brain CT or MRI scan 3	X (within 28 days)						
Imaging Evaluation 4	X (within 28 days)			X (every 6 weeks) -----			
Hematological examination 5	X (within 7 days)		X	X	X		
Complete Set of Biochemical Tests 6	X (within 7 days)		X	X	X		
Urine test 7	X (within 7 days)		X	X	X		
Fecal Test 8	X (within 7 days)			X (every 6 weeks) -----			
Serum pregnancy test	X (within 7 days)						
Study of drug use		X	X	X	X		
Evaluation of Adverse Events (AEs)				-----(
comorbidities and concomitant medications				-----(

1. Complete medical history, demographic data, surgical history, concomitant medications, comorbidities, allergy history, and smoking history.
2. Complete physical examination, ECOG performance status score, height, weight, vital signs, and detailed examinations of all body systems.

3. Head CT/MRI scans are only required for patients with baseline neurological symptoms to exclude brain metastases.
4. Tumor assessment during the treatment phase is required every 6 weeks. After treatment completion, imaging evaluations are required every 8 weeks until disease progression occurs. If a patient withdraws from the study due to disease progression, no additional CT scans are required during the final follow-up at study completion.
5. Hematological tests include: hemoglobin, hematocrit, platelets, white blood cells, absolute neutrophil count, and absolute lymphocyte count, which can be performed 1 day prior to the start of each treatment course.

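### Protocol 3.7.3.2 sets a minimum age of 28 days for the baseline scan, counted from enrollment, while 3.8.1 and the flowchart set a maximum of 28 days, and the two rules can almost never both be met

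*Protocol*

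**What the plan says.** Four places in the protocol bear on when the baseline scan is taken.

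- **Section 3.7.3.2 (Imaging Evaluation), screening period:** "A CT or MRI scan of the chest and abdomen must be performed at least 28 days prior to enrollment". The verb is mandatory and the anchor is enrollment.
- **Section 3.8.1 (Screening Period):** "At least one CT or MRI scan of the target lesion, which can be performed within 28 days prior to initiating the investigational drug". The anchor is the first study drug.
- **Section 7.5 (flowchart), imaging row, screening column:** the entry begins "X (within 28 days". The cell names no anchor.
- **Section 3.7.3.1 (Research Visits):** "Screening visit should be conducted within 28 days prior to initiation of study drug therapy". This is the visit to which the scan belongs.

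Two endpoint definitions use the scan as their reference. Section 7.3 defines partial response as "A reduction of at least 30% in the sum of LD values at the target lesion compared to baseline total LD". Section 3.7.1 says of depth of response (DpR): "This refers to the percentage of maximum tumor shrinkage achieved during treatment compared to baseline". Progression in 7.3 has a different reference: the smallest sum recorded since treatment began, or a new lesion.

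**The concern.** Section 3.7.3.2 is the dedicated imaging section, and it points the opposite way from the other three places. It sets a floor on scan age where they set a ceiling, and it counts from a different date. An investigator who complies with 3.7.3.2 will normally deviate from 3.8.1, and the reverse. A monitor has no rule for deciding which scan is in window.

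The scan supplies the denominator for PR, and so for most of what can count towards the primary endpoint, ORR. It is also the denominator for DpR. A scan that is old at first dose does not describe the tumour being treated. If the tumour has grown in the meantime, part of any real shrinkage is spent on returning to the old measurement before a response starts to register.

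**Working it through.** **1. The plan's own figure.** The sample size of 37 rests on ORR 50% against 70%, one-sided alpha 0.05 and power 0.80. Exact enumeration of Simon two-stage designs gives a minimax design with 23 patients in stage 1 (continue if more than 12 respond) and 37 in total (success if more than 23 respond). Its alpha is 0.0482 and its power 0.801. So 37 reproduces, and it does not depend on the scan window.

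**2. Can both windows be met?** Let k be the days from enrollment to first dose (k ≥ 0), and A the scan's age in days at first dose.

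- Section 3.7.3.2: the scan is at least 28 days before enrollment, so A ≥ 28 + k.
- Section 3.8.1: A ≤ 28.
- Both require 28 + k ≤ A ≤ 28, which has a solution only for k = 0 and A = 28.

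| k (days) | Minimum A under 3.7.3.2 | Maximum A under 3.8.1 | Compatible? |
|---|---|---|---|
| 0 | 28 | 28 | only at exactly day -28 |
| 1 | 29 | 28 | no |
| 7 | 35 | 28 | no |
| 14 | 42 | 28 | no |

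**3. What an old scan does to PR and DpR.** Suppose the sum of diameters grows by a fraction g between the scan and first dose. The protocol gives no value for g, so those below are assumptions. With baseline sum B, the sum at first dose is B(1+g).

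- PR is recorded when the sum falls to 0.7B. The true shrinkage from first-dose size that this needs is 1 − 0.7/(1+g).
- A true shrinkage of 30% from first-dose size is recorded as a DpR of 1 − 0.7(1+g).

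| Assumed g | True shrinkage needed for PR | DpR recorded when true shrinkage is 30% |
|---|---|---|
| 0% | 30.0% | 30.0% |
| 5% | 33.3% | 26.5% |
| 10% | 36.4% | 23.0% |
| 15% | 39.1% | 19.5% |

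For example, at g = 10%: 1 − 0.7/1.10 = 0.364, and 1 − 0.7 × 1.10 = 0.23.

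**4. Progression.** PD needs a 20% rise over the smallest sum since treatment began. Once a tumour has shrunk below its baseline, the baseline no longer sets that reference. For a patient whose tumour does not shrink and whose baseline is the reference, the rise from first-dose size that triggers PD is 1.2/(1+g) − 1: 14.3% at g = 5% and 9.1% at g = 10%, instead of 20%.

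**The case against.** The strongest reply is that 3.7.3.2 contains a drafting or translation slip for a 28-day maximum. Three other places state that limit, and the trial is described as single-center, so in practice staff may simply use the 28-day cap. This has force. The absence of an upper limit is a property of 3.7.3.2 read alone, and nothing shows that the sponsor chose an uncapped baseline. But the sentence is current text, it is mandatory where 3.8.1 is permissive, and no rule of precedence is given. The contradiction stands. Its consequence depends on which sentence is followed.

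Stronger readings are tempting, and the documents do not support them.

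- **A large loss of power.** Suppose best percentage change is normal with SD 25 points, 70% of patients reach a 30% reduction from a fresh scan, every patient has an old scan, and success is at least 24 of 37. Growth of 5%, 10% or 15% would then lower ORR to 65%, 61% or 56%, and power from 0.81 to 0.59, 0.36 or 0.19. Growth, SD and the share of patients affected are all assumptions. If only a quarter of patients were affected, with 10% growth, ORR would be about 67.7% and power about 0.71. The comparison is also with a scan after which nothing grows, which a 28-day maximum does not guarantee. These figures illustrate a direction and do not estimate an effect.
- **All responses are affected.** Complete response in 7.3 is disappearance of all tumour evidence, not a percentage change. Only PR and DpR use the baseline sum.
- **PFS is generally shortened.** By step 4 of the working, the effect falls mainly on patients without shrinkage.
- **The imaged field contradicts the appendix because the pelvis is missing.** Section 7.3 says of CT/MRI that "This method is suitable for the chest, abdomen, and pelvis". That describes where the technique works and does not prescribe a field, so it does not conflict with 3.7.3.2. Section 3.8.1 in any case requires imaging of the target lesion, wherever it lies.

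**Conclusion.** The point holds as a contradiction in operative text. Section 3.7.3.2 conflicts with 3.8.1 and the flowchart on the direction of the limit, and with 3.8.1 and 3.7.3.1 on the anchor date. It conflicts with 3.8.1 for every patient first dosed one day or more after enrollment.

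The effect on results is conditional. It arises if 3.7.3.2 is followed literally and tumours grow between scan and first dose. It would then bias ORR and DpR downward, against the treatment. For assumed growth of 5% to 15%, a recorded PR would need a true shrinkage of 33.3% to 39.1%. The size of the bias in ORR, and any loss of power, cannot be derived from the documents. It should be corrected because the scan underlies the primary endpoint and the correction is nearly free.

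**What to change.** Reword the screening item of 3.7.3.2 so that it gives a maximum scan age counted from first study drug, as 3.8.1 does. State the same anchor in the imaging row of the flowchart, and check that 3.7.3.1, 3.7.3.2, 3.8.1 and 7.5 then give one window and one date. No endpoint, analysis or sample size changes. The cost is one protocol sentence and a flowchart label. If patients have already been scanned, list each scan's age at first dose, so that the number outside the reconciled window is known before the ORR analysis.

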3.8 Research Process

3.8.1 Screening Period

within 28 days prior to initiating the study drug

- Sign an informed consent form before any research-related procedure is performed;
- baseline 12-lead electrocardiogram (ECG) examination;
- Brain CT or MRI scans should only be performed when neurological symptoms are present (indicating brain metastases).
- Tumor assessment at baseline: At least one CT or MRI scan of the target lesion, which can be performed within 28 days prior to initiating the investigational drug.

Screening period – within 7 days prior to initiating study drug therapy

- Record/confirm the tumor stage at the time of diagnosis.
- Demographic information, complete medical history, and surgical history, including previous anticancer treatments.
- A complete physical examination (PE), including the ECOG general condition score, height, weight, and a detailed systemic examination.
- Signs and symptoms (including heart rate, blood pressure, respiratory rate, and body temperature).
- Record all comorbidities and concomitant medications with their indications.
- Complete blood count (CBC): hemoglobin, platelet count, white blood cell count and differential, including absolute counts of neutrophils and lymphocytes.
- Complete blood biochemistry panel: including blood glucose, calcium, phosphorus, sodium, potassium, chloride, creatinine, blood urea nitrogen

(BUN), total protein, albumin, alanine aminotransferase (ALT), aspartate aminotransferase (AST), alkaline phosphatase, total bilirubin, etc.

- Urinary pregnancy tests should be performed for all women of childbearing age. Women who have been postmenopausal for at least 1 year or have undergone sterilization procedures are not required to undergo pregnancy testing.
- Urinalysis: Includes urine leukocytes, urine red blood cells, urine glucose, urine protein, and occult blood
- Routine stool examination

3.8.2 Treatment Period

The treatment period is defined as a 21-day cycle. Therapeutic efficacy is evaluated every 2 cycles. Laboratory tests and imaging assessments during the treatment phase are detailed in the flowchart.

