3.4 Study Duration

Based on an estimated enrollment of approximately 5 patients per month, the enrollment period would require approximately 8 months. The total study duration is estimated to be around 12 months.

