3.5 Subject Withdrawal from the Study

Discontinued cases refer to patients who cease medication for various reasons during clinical studies. Patients meeting the following criteria will be withdrawn from the study:

- The patient or their legal representative requests withdrawal;
- According to the investigators 'opinion, continued participation in the study would be harmful to the patient's health.
- patients with severe non-adherence or serious protocol violations;
- The patient is pregnant, and pregnancy should be reported as a serious adverse event.
- When other diseases occur concurrently during the study, and based on the investigator's assessment that the disease will significantly affect the evaluation of the patient's clinical condition, and when discontinuation of the current treatment regimen is required;
- other malignancies requiring treatment;
- lost to follow-up;

- Use of prohibited drugs or other drugs that the investigator judges may cause toxic reactions or bias the results of the study;
- The patient died.

All patients who withdraw from the study should have the reason for withdrawal recorded in the case report form and the patient's medical record.

All patients who withdrew due to adverse events or abnormal laboratory findings should be followed up until the adverse event resolved or stabilized, with subsequent outcomes recorded. If a patient died during the trial or within 30 days after trial completion, the investigator must be notified by the researchers. The cause of death must be documented in detail on the Serious Adverse Event (SAE) report form within 24 hours.

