3.6 Treatment Plan

3.6.1 Treatment Arrangements

Treatment regimen: Anlotinib, orally, 12 mg once daily, administered from day 1 to day 14 of each cycle, with each cycle lasting 3 weeks; Sintilimab, 200 mg, intravenous infusion for 1 hour \pm 5 minutes, administered every 3 weeks until disease progression or intolerable adverse reactions occur.

Treatment should be continued until disease progression or intolerance is achieved. Due to the inherent limitations of the RECIST criteria used for efficacy evaluation, if imaging suggests disease progression but the study physician determines that the patient has clinical benefit, treatment may still be continued.

The efficacy was evaluated every 6 weeks.

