6.4 Reporting of Serious Adverse Events

From the time of informed consent signing until 30 days after the completion of the last dose, any defined serious adverse event (SAE), including laboratory test abnormalities meeting the SAE definition, must be immediately reported to the designated personnel in the study documents (within 24 hours of the investigator's knowledge). The SAE report form must also be completed and submitted to the designated personnel in the study documents within 24 hours of the investigator's knowledge.

Each serious adverse event should be followed up until resolution or stabilization,

with an updated report submitted to the designated personnel. A simple Level 4 laboratory test abnormality (according to the CTCAE 5.0 criteria) should not be reported as a serious adverse event unless the investigator determines that the abnormality meets the International Conference on Harmonisation (ICH) criteria for serious adverse events (as defined in Section 6.3.2). A Level 4 laboratory test abnormality that occurs at baseline and is a manifestation of the disease according to the CTCAE 5.0 criteria should not be reported as a serious adverse event, particularly if the abnormality is present but the patient is still allowed to enroll or is not excluded from enrollment. If there is any doubt about whether the abnormality should be reported as a serious adverse event, the investigator may consult the study monitor. A Level 4 laboratory test abnormality should be recorded on the "Laboratory Data" page and regularly cross-checked by the medical monitor.

According to the requirements of local laws and regulations, serious adverse events must be reported to the ethics committee and the drug regulatory authority.

7. Appendix

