6. The complete biochemical panel includes: blood glucose, calcium, phosphorus, sodium, potassium, chloride, creatinine, blood urea nitrogen, total protein, albumin, alanine aminotransferase (ALT), aspartate aminotransferase (AST), alkaline phosphatase (ALP), and total bilirubin. These tests can be performed one day prior to the start of each treatment course.
7. Urinalysis includes: urine specific gravity, pH value, urine glucose, urine protein, and occult blood. Screening requires laboratory urinalysis, followed by urine test strips during subsequent treatment courses. Urinalysis can be performed one day before the start of each treatment course.
8. Fecal examination, also known as routine stool test, includes fecal occult blood, white blood cells, and red blood cells. It is performed once during the screening phase and can be conducted concurrently with each subsequent tumor assessment.
9. Follow-up should be conducted every 3 months after disease progression until 1 year after progression or death.

8. References

- [1] Bray Freddie, Laversanne Mathieu, Sung Hyuna, et al. Global cancer statistics 2022: GLOBOCAN estimates of incidence and mortality worldwide for 36 cancers in 185 countries. *CA Cancer J Clin.* 2024. 74(3): 229-263.
- [3] Tejpar Sabine, Stintzing Sebastian, Ciardiello Fortunato, et al. Prognostic and Predictive Relevance of Primary Tumor Location in Patients With RAS Wild-Type Metastatic Colorectal Cancer: Retrospective Analyses of the CRYSTAL and FIRE-3 Trials. *JAMA Oncol.* 2017. 3(2): 194-201.
- [4] Venook Alan P, Niedzwiecki Donna, Lenz Heinz-Josef, et al. Effect of First-Line Chemotherapy Combined With Cetuximab or Bevacizumab on Overall Survival in Patients With KRAS Wild-Type Advanced or Metastatic Colorectal Cancer: A Randomized Clinical Trial. *JAMA.* 2017. 317(23): 2392-2401.
- [5] André Thierry, Falcone Alfredo, Shparyk Yaroslav, et al. Trifluridine-tipiracil plus bevacizumab versus capecitabine plus bevacizumab as first-line treatment for patients with metastatic colorectal cancer ineligible for intensive therapy (SOLSTICE): a randomised, open-label phase 3 study. *Lancet Gastroenterol Hepatol.* 2023. 8(2): 133-144.

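### Pregnancy requires withdrawal and SAE reporting, but the schedule of assessments has a pregnancy test at screening only and none during open-ended treatment

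*Protocol*

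**What the plan says.** Protocol section 3.5 lists pregnancy among the reasons for withdrawal: "The patient is pregnant, and pregnancy should be reported as a serious adverse event". The exit criteria in the synopsis say the same.

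Section 3.8.2 does not list the on-treatment tests itself but refers to the table in 7.5: "Laboratory tests and imaging assessments during the treatment phase are detailed in the flowchart". In that table the row "Serum pregnancy test" has one mark, in the screening column, within 7 days. The haematology, biochemistry and urine rows are also marked at cycle 2, at later cycles and at the post-treatment visit.

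Note 7 to the table defines the repeated urine test: "Urinalysis includes: urine specific gravity, pH value, urine glucose, urine protein, and occult blood". It also allows flexible timing: "Urinalysis can be performed one day before the start of each treatment course".

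Section 3.6.1 sets no fixed number of cycles: "Treatment should be continued until disease progression or intolerance is achieved".

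The protocol has other safeguards. Section 3.3.1 requires a negative pregnancy test in the 7 days before treatment, and contraception during the study. Section 3.3.2 excludes women who are pregnant or planning to conceive. Section 6.2 requires close adverse event monitoring, and section 3.8.4 allows unscheduled visits when clinically needed.

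**The concern.** The protocol names pregnancy as an event that must end participation, but schedules nothing after screening that would detect it. If contraception failed during treatment, the pregnancy would come to light only through symptoms, self-report or general adverse event enquiry. Until then the patient could go on receiving anlotinib, sintilimab and 6-weekly imaging, and the protocol's own withdrawal rule would be applied late. What is at stake is the safety of individual patients, not the statistical conclusions.

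**Working it through.** The protocol gives no figure to reproduce. The check is a reading of the schedule, followed by a short count for scale.

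**Scheduled pregnancy tests**

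| Place in the protocol | Pregnancy test required |
|---|---|
| 3.3.1, eligibility | Yes, within 7 days before treatment |
| 3.8.1, screening list | Yes, urine, within 7 days |
| 7.5, screening column | Yes, serum, within 7 days |
| 7.5, cycle columns | No mark |
| 7.5, post-treatment visit | No mark |
| 7.5, follow-up columns | No mark |
| 7.5, note 7 (repeated urine test) | Not a component |
| 3.8.4, unscheduled visits | Not named |

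The eligibility and screening entries describe the same time point, so the count is one test at screening and none afterwards. The table also shows that 3.8.1 asks for a urine test where 7.5 asks for serum.

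**Illustration of scale**

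Inputs: 21-day cycles (3.6.1 and 3.8.2), accrual of about 8 months (3.4), and from the same section "The total study duration is estimated to be around 12 months". One month is taken as 365.25 / 12 = 30.4375 days. Treatment is assumed to continue to study end without dose delays.

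- First patient enrolled: 12 × 30.4375 = 365.25 days. Day-1 visits after cycle 1: 365.25 / 21 = 17.4, so 17. The screening test could be up to 365 + 7 = 372 days old at study end.
- Last patient enrolled: 12 − 8 = 4 months, or 4 × 30.4375 = 121.75 days. Day-1 visits after cycle 1: 121.75 / 21 = 5.8, so 5. The screening test could be up to 122 + 7 = 129 days old.

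With a test at each cycle, the longest gap would be 7 + 21 = 28 days from screening to cycle 2 and about 21 days after that, or longer when a dose is delayed.

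These counts are one scenario. The synopsis gives a total duration of about 1.5 years, of which January to June 2027 is set aside for data cleaning and analysis, so the two stated timelines differ. Patients who stop early for progression or intolerance have fewer visits under either timeline.

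**The case against.** The strongest reply is that this is an omission, not a contradiction. A withdrawal criterion does not by itself call for a scheduled test: section 3.5 also lists other malignancies and intercurrent disease, and neither has a dedicated test. A screening test, mandatory contraception and withdrawal on occurrence make a coherent, if minimal, scheme. That is fair, and it is why the point is a recommendation. It still stands, because the protocol itself fixes the on-treatment laboratory schedule in 7.5. Contraception lowers the chance of pregnancy but does not detect a failure, and an unscheduled visit needs a prior suspicion.

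It is also true that nothing in the protocol describes the reproductive toxicity of either drug or sets a testing interval. Testing at every cycle is a judgement, made because the patient attends and gives urine then anyway.

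A third objection is that the table may be damaged in the available copy, which shows no cycle 3 column and cuts off the adverse event rows. This lowers certainty only slightly: neighbouring rows kept their on-treatment marks, and neither the text nor the notes mention a repeat test.

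A reader might infer three stronger things, and the documents support none of them:

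- That SAE reports would be late. Section 6.4 starts the clock at awareness: "within 24 hours of the investigator's knowledge". Detection may be delayed, but the report need not be.
- That a number of pregnancies can be expected. The protocol does not say how many of the 37 patients will be women of childbearing age, and 3.8.1 exempts postmenopausal and sterilised women.
- That the primary analysis is compromised. The response rate, sample size and error rates do not depend on this schedule.

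**Conclusion.** The point holds as a low-severity patient-safety improvement. Followed as written, the protocol has one pregnancy test before treatment and none on treatment, at its end or in follow-up, while pregnancy is an event that must stop participation. The largest illustrative gap is 17 day-1 visits without a test. It rests on 3-week cycles kept on time and treatment for the whole 12 months of section 3.4, so it should not be read as typical. The number of women affected is unknown and may be small.

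**What to change.** For women of childbearing age, add to the table in 7.5 a urine pregnancy test before dosing on day 1 of each cycle from cycle 2 and at the post-treatment visit, using the urine already collected under note 7.

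Add a rule for a positive strip: hold dosing until a confirmatory test is available. If a response scan falls due meanwhile, use MRI, which 3.7.3.2 already permits, or scan promptly once pregnancy is excluded, so that the window of 6 weeks ± 5 days is kept. Without this provision, holding CT could move a primary endpoint assessment outside its window.

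As an editorial change, name the same screening assay in 3.8.1 (now urine) and 7.5 (now serum).

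The cost is one strip per cycle from cycle 2 plus one post-treatment. That is 17 + 1 = 18 for a woman treated for the full 12 months, and about 2 to 3 for one who stops at the first 6-week scan. No visit or sample is added. A false positive would occasionally cause a short delay to a dose or scan.
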